## DOCUMENT HISTORY

Version	Date of Issue	Summary of Changes
1.0	17 Sep 2018	Initial Version
2.0	21 Nov 2018	Investigator agreement page and throughout protocol: Replaced CTCC with CHeT when describing study site
2.0	21 Nov 2018	List of Abbreviations – added VC (video conference) and API (application program interface)
2.0	21 Nov 2018	Protocol Synopsis, Sections 4.2 and 5.1 – Added language to allow subjects from STEADY PDIII and SURE PD3 who declined consenting to future contact the ability to directly contact UR to request information about participating in AT-HOME PD
2.0	21 Nov 2018	Schedule of Activities and Section 5.5.2 – replaced tele-visit with video conference to describe the screening visit
2.0	21 Nov 2018	Schedule of Activities and Section 5.5.3 – Removed smartphone app registration from the list of activities performed at the baseline visit and added language to allow for registration in Synapse web portal to occur just prior to the visit date
2.0	21 Nov 2018	Section 1.1 – Updated the length of time DAT scan follow-up that will be conducted in SURE-PD3 to over a length of 1 to 2 years.
2.0	21 Nov 2018	Section 5.1 – Revised language regarding contacting SURE-PD3 subjects to allow contact after completion of SURE-PD3 study
2.0	21 Nov 2018	Sections 5.1 and 8 – Replaced subject payment method from debit card to check and added language offering additional standard internet and/or smartphone/data plan reimbursement for minorities.

Version	Date of Issue	Summary of Changes
2.0	21 Nov 2018	Sections 5.1, 5.5.1, 5.5.2, and 5.5.3 – Revised the window of timing for contacting SURE-PD3 participants and completing the prescreen call, screening video conference, and baseline tele-visit and replaced the description of the last in-person SURE-PD3 study visit from “on-drug” to “final visit (or equivalent) in the planned treatment period”
2.0	21 Nov 2018	Section 5.2 – Removed language stating CTCC team member will email reminders to participants to eConsent, revised language to specify screening visit will be scheduled during prescreen call, and added language to state AHPD staff may email participant the current UR IRB approved consent form, if requested during the prescreen call
2.0	21 Nov 2018	Section 5.4 – Revised to reflect REDCap entries will be created on all participants AHPD study team establishes direct contact with
2.0	21 Nov 2018	Section 5.5.1 – Clarified delivery method and timing of eConsent and technology survey
2.0	21 Nov 2018	Section 5.5.2 – Modified duration of screening visit to approximately 30 minutes
2.0	21 Nov 2018	Section 5.5.2 – Modified the list of information required for creating a participant’s FI account and updated the description of events occurring if a participant is already enrolled in FI
2.0	21 Nov 2018	Section 5.5.4 – Removed SMS as the means of notification method for mPower reminders

Version	Date of Issue	Summary of Changes
2.0	21 Nov 2018	Section 6.1.3 – Removed sentences from MDS-UPDRS Part III stating that subjects on symptomatic dopaminergic therapy will be asked to (optionally) hold their morning dose during visit days
2.0	21 Nov 2018	Section 12 – Removed “enactment of Medical Safety Escalation Plan” from the list of reportable events and added a statement below that it should be reported to the CTCC PM
2.0	21 Nov 2018	Section 15.5 – Replaced “de-identified” with “transformed” to describe the transferred dataset
2.0	21 Nov 2018	Section 15.5 – Updated the description of tele-visit REDCap data access to state Sage Bionetwork access via API
2.0	21 Nov 2018	Section 17.2 – Added process of entering data during REDCap downtime via collection on paper CRFs
2.0	21 Nov 2018	Administrative changes throughout
3.0	06 Nov 2019	Replacement of [name] with [name] as a principal investigator
3.0	06 Nov 2019	Replacement of [name] with [name] as listed collaborator from MJFF
3.0	06 Nov 2019	Updated Steering Committee List
3.0	06 Nov 2019	Updated Acronyms List with addition of PD-PROP and SUPER-PD
3.0	06 Nov 2019	Protocol Synopsis and Section 13.4 – updated sample size determination and true concordance for SURE-PD3 and combined SURE-PD3 and SUPER-PD participants expected to complete at least one TV close in time to their in-person clinic visit.
3.0	06 Nov 2019	Updated Figures 1 and 2 with added data flow description from DMR to Qualified Researchers and added Figure 1a

Version	Date of Issue	Summary of Changes
3.0	06 Nov 2019	Addition of SUPER-PD sub-study throughout
3.0	06 Nov 2019	Administrative Changes Throughout

**Table 1. List of abbreviations and definition of terms**

Abbreviation or specialist term	Definition
ADAGIO	Attenuation of Disease Progression with Azilect Given Once-daily
AE	Adverse Event
AHPD	AT-HOME Parkinson's Disease
API	Application Program Interface
AUC	Area under the concentration-time curve
CAPA	Corrective and Preventive Action Plans
CDEs	Common Data Elements
CFR	Code of Federal Regulations
CGI-S	Clinician Global Impression – Severity
CHeT	University of Rochester Center for Health + Technology
CNS	Central Nervous System
Co-I	Co-Investigator
CRA	Clinical Research Associate
CRF	Case Report Form
CTCC	Clinical Trials Coordination Center
DAT	Dopamine transporter
DATATOP	Deprenyl And Tocopherol Antioxidative Therapy Of Parkinsonism
DM	Data Management
DMR	Data Management Resource
ECG	Electrocardiogram
eCRF	Electronic Case Report Form
EDC	Electronic Data Capture
EDL	Experiences of Daily Living
ET	Early Termination
FDA	Food and Drug Administration
FI	FoxInsight
GCP	Good Clinical Practice
GPS	Global Positioning System
GUID	Global Unique Identifier
HIPAA	Health Insurance Portability and Accountability Act
HSP	Human Participant Protection Program

Abbreviation or specialist term	Definition
ICC	Intra-class correlation
ICD	International Classification of Diseases
ICF	Informed Consent Form
ICH	International Conference on Harmonisation
ICJME	International Committee of Medical Journal Editors
ID	Identification Number
IR	Immediate Release
IRB	Institutional Review Board
ITT	Intent-to-treat
IV/WRS	Interactive Voice/Web Response System
LONI	Laboratory of Neuro Imaging
MDS-UPDRS	Movement Disorders Society-Unified Parkinson's Disease Rating Scale
MedDRA	Medical dictionary for Regulatory Activities
MGH	Massachusetts General Hospital
MJFF	Michael J Fox Foundation for Parkinson's Research
MMSE	Mini-Mental State Exam
MoCA	Montreal Cognitive Assessment
NINDS	National Institute of Neurological Disorders and Stroke
NW	Northwestern University
ORPA	Office of Research and Project Administration
PD	Parkinson's Disease
PD-PROP	Parkinson Disease Patient Reported Outcome of Problems
PDBP	Parkinson's Disease Biomarkers Program
PDF	Portable Document Format
PGI	Patient Global Impression
PI	Principal Investigator
PM	Project Management
PP	Per Protocol
PPMI	Parkinson's Progression Markers Initiative
PRO	Patient Reported Outcomes
PSC	Protocol Steering Committee
PSG	Parkinson Study Group

Abbreviation or specialist term	Definition
PT	Preferred Term
PW	Premature Withdrawal
QA	Quality Assurance
QC	Quality Control
RE	Reportable Events
REDCap	Research Electronic Data Capture
ROC	Receiver Operating Characteristic Curve
RSRB	Research Subjects Review Board
SA	Specific Aim
SAE	Serious Adverse Event
SAP	Statistical Analysis Plan
SC	Steering Committee
SD	Standard Deviation
SE	Standard Error
SEADL	Schwab & England Activities of Daily Living Scale
SMC	Safety Monitoring Committee
SOA	Schedule of Activity
SOC	System Order Class
SOP	Standard Operating Procedure
SP	Smartphone
ST	Symptomatic Dopaminergic Therapy
SUPER-PD	Sensor Use to Monitor Progression and Evaluate Symptoms Remotely in Parkinson's Disease
TBI	Traumatic Brain Injury
TV	Tele-visit
UPDRS	Unified Parkinson's Disease Rating Scale
UR	University of Rochester
URMC	University of Rochester Medical Center
USC	University of Southern California
VC	Video Conference


Objectives
	
1. To establish and implement an infrastructure for longitudinal remote follow-up of phase 3 trial cohorts:
 
 
a. Transition from site-based to a centralized site and coordination center to manage all participant activity in virtual extensions of SURE-PD3, with projected enrollment of <math>\geq 70\%</math> of final trial cohorts, and core data collection in accordance with Parkinson’s Disease Biomarkers Program (PDBP) schedule of activities.
 
b. Conduct an annual research visit (tele-visit) program and establish the feasibility and cross-sectional reliability of tele-visit versus in-person visit assessments in a subset of STEADY-PD III and SURE-PD3 participants.
 
c. Deploy a smartphone application, based on the mPower study, for remote data collection in a clinical trial cohort as preliminarily characterized in the Smart4SURE sub-study of SURE-PD3.
 
d. Establish a mechanism for linking STEADY-PD III and SURE-PD3 study data with data collected through smartphone-based assessments, tele-visits, and Fox Insight (FI), a separate longitudinal patient-reported outcomes (PROs) online research study.
 
 
2. To compare patient-driven (smartphone, web-based surveys) vs clinician-driven (tele-visit) outcomes by:
 
 
a. Correlating the smartphone and tele-visit platforms’ component and composite features, and their changes over years.
 
b. Comparing the smartphone and tele-visit platforms’ abilities to: i) measure PD progression and predict clinical events and changes in PROs; ii) distinguish rapid vs slow progressors based on baseline Movement Disorders Society-Unified Parkinson’s Disease Rating Scale (MDS-UPDRS) scores, dopamine transporter (DAT) deficit (in SURE-PD3) or serum urate levels (in STEADY-PD III); iii) demonstrate persistence of any effects of isradipine or inosine in their respective trials.
 
c. Comparing completion status and performance on FI and tele-visit PROs.
 
 
3. To explore novel smartphone-based real-life mobility biomarkers of PD disability and its progression that are normally inaccessible with traditional office measures. We will investigate the ability of passively collected smartphone data on ambulation and location to enable assessments of physical activity and

	socialization that correlate with motor and non-motor functions.
Study/Observation Period	24 months (with rolling enrollment), after completion of the interventional phases of STEADY-PD III and SURE-PD3
Study Population	
All individuals with early idiopathic PD enrolled in the STEADY-PD III (NCT02168842) and SURE-PD3 (NCT02642393) studies (N≈600) who have consented to be contacted for future research will be asked to participate or if a subject from these two studies directly contacts the University of Rochester (UR) to request information about study participation.
 
We expect approximately 70% of STEADY-PD III and SURE-PD3 participants (N≈420) are expected to consent and participate in at least the tele-visit portion of the study.
 
We expect approximately 80% of individuals who enroll in this study (N≈340) to participate in the smartphone portion (and thus the smartphone vs tele-visit comparison) of the study.
 
We expect approximately 70% of individuals who participate in the smartphone portion of the study (N≈240) to consent to passive collection of motor and mobility data.
 
We expect approximately 80% of individuals who enroll in this study (N≈340) to participate in the FI portion of the study.

Study Design	Observational study to characterize and compare long-term clinical outcomes data collected remotely through annual tele-visits, quarterly interactive smartphone app sessions, and web-based surveys in individuals with PD who have completed the interventional phases of STEADY-PD III and SURE-PD3 clinical trials.
Number of Participants	Approximately 420
Main Inclusion Criteria	
 
1. Enrollment in STEADY-PD III or SURE-PD3 studies
 
2. Prior consent to be contacted by the University of Rochester (UR) or if a subject from STEADY-PD III or SURE-PD3 studies directly contacts UR to request information about study participation
 
3. Internet-enabled device that will support participation in tele-visits
 
4. Have created or willing to create a Global Unique Identifier (GUID)
 
5. Willing and able to provide informed consent
 
6. English fluency
 
7. For participants opting to participate in the smartphone component, possession of a suitable smartphone (iPhone
 

	or Android) with adequate data plan and cellular network access/signal or Wi-Fi access
Main Exclusionary Criteria	1. Inability to carry out study activities as determined by study staff
Study background and Rationale	At the launch of AT-HOME PD the STEADY-PD III and SURE-PD3 trials were active NINDS-funded phase 3 studies of potential disease-modifying interventions in PD. The long-term observation of participants from these trials, while challenging to implement, was deemed a valuable research opportunity. The reliance on in-person visits and snapshot assessments in a condition characterized by variable symptoms is an important limitation. Tele-visit, web-based surveys, and smartphone-based remote sensor assessments represent particularly promising methods for streamlining study conduct, reducing participant burden, and enabling the collection of data beyond the usual episodic, in-clinic assessments. The objective of this study is to leverage modern technology to develop, pilot and implement a 100% virtual model for long-term follow-up utilizing tele-visit and smartphone platforms for quantitative monitoring of clinician- and patient-reported outcomes (PROs).
Study Platforms and Outcome Measures	
Tele-visit platform – Participants will complete a total of three tele-visits, which will occur at baseline, month 12, and month 24. Some activities will be completed either prior to or post tele-visit by the participant. Assessments will include:
 
 
• Review of reportable events
 
• Review of concomitant medications
 
• MDS-UPDRS parts 1a, 3, and 4 (where applicable)
 
• Montreal Cognitive Assessment (MoCA)
 
• Schwab & England Activities of Daily Living Scale (SEADL)
 
• Clinician Global Impression and Patient Global Impression – Severity and Change
 
• Determination of Falls
 
• Performance of one complete set of active motor and cognitive smartphone application tasks (when applicable)
 
• Review of completion of MDS-UPDRS parts 1b and 2, self-reported falls, and patient global impression – severity and change (with direct link to survey sent ahead of visit)
 
• Review of compliance with smartphone tasks and FI assessments where applicable
 
• Preference and Burden Survey
 

	
Investigators administering MDS-UPDRS part 3 (motor examination) will be neurologists or nurse practitioners who have obtained formal MDS-UPDRS certification and will have additionally undergone joint training to reconcile scoring differences and minimize inter-rater variability. Tele-visits will be scheduled in either the morning or afternoon according to participant preference and, for participants on symptomatic dopaminergic therapy, the MDS-UPDRS will be preferably performed in the usual ON state.
 
FI web-based survey platform – Participants will be asked to complete a set of standard questionnaires every 3 months through an online observational companion study called FI. Study participants will be encouraged but not required to participate in FI. Standard assessments include:
 
 
• The Parkinson’s Disease Questionnaire, short-form 8 item version (PDQ-8)
 
• MDS-UPDRS part 2
 
• Physical Activity Scale for the Elderly (PASE)
 
• Your Cognition and Daily Activities (PDAQ-15)
 
• Euroqol Five (EQ-5D)
 
• Non-motor symptoms questionnaire (NMS-QUEST)
 
• Geriatric Depression Scale, short form (GDS)
 
• Parkinson’s Disease-Patient Reported Outcomes of Problems (PD-PROP)
 
 
Participants are invited to complete additional PRO surveys about, but not limited to, symptoms, disease progression, quality of life, patient preference or general health.
 
Smartphone session platform (mPower-based app) – We will use mPower 2.0 developed by Sage Bionetworks on both iOS and Android. mPower will include active tasks to be completed (Scientific Aim (SA) 2) and allow passive collection of motor and mobility data with participant permission (for SA3). 14-day smartphone sessions will occur every 3 months. During these sessions, participants will complete smartphone-based motor tasks daily on at least 10 days and cognitive assessments on at least 3 days. Given diurnal variation in active task performance, participants will be asked to select morning or afternoon as their preferred window for completion and to consistently complete the active tasks according to their selected preference.
 
Motor Tasks:
 
 
• Gait task - a 30 second walk
 
• Finger tapping task - 30 seconds of rapid finger tapping in each hand
 

--	---

	
 
• Resting tremor task - 30 seconds of holding phone in each hand
 
• Balance task - 30 seconds of standing still
 
 
Cognitive Assessments:
 
 
• Digit span
 
• Digit symbol substitution
 
• Spatial working memory
 
 
Enrolled participants will also use the application to track their medication adherence relative to tasks and, optionally, self-reported symptoms and triggers. For those participants who optionally consent to passive data collection, the smartphone application will collect multiple streams of passive data including: movement patterns captured by location services on phone and walking patterns captured by accelerometer gyroscope, and pedometer.

Study Compliance	
Compliance with all three study platforms will be monitored. CHeT/CTCC will monitor compliance through tele-visits and patient interview during the visit. Sage Bionetworks will utilize push notifications and Short Message Service (SMS) reminders to encourage compliance with smartphone-based assessments. MJFF will send automated e-mail reminders to complete the quarterly assessments after approximately 45 days and again after approximately 88 days. CHeT/CTCC will receive quarterly compliance reports from Sage Bionetworks and from MJFF (until a publicly-accessible research dashboard becomes available through University of Southern California’s Laboratory of Neuro Imaging (LONI)).

Data Management	
 
1) Data collected during tele-visits will be entered and maintained in REDCap (a secure web-based survey and data management system) and transferred to Synapse (an open source collaborative platform, for analysis).
 
2) Survey data collected by FI will be exported to LONI (a secure online neuroscience dataset sharing system of USC’s) and then to Synapse.
 
3) Data collected from smartphones will be transferred to the Sage Bionetworks maintained Bridge server and then to Synapse.
 
4) All platform data will be transferred from Synapse to PDBP-DMR All data will be identified by the GUID, the date, time of the visit, and then transferred to the Sage Bionetworks managed Synapse. From Synapse the cleaned, processed, and event date and time transformed dataset will be transferred to the PDBP’s Data Management Resource (DMR) for further distribution to PDBP investigators and will be made available to the wider research community through their qualified researchers program [See Resource Sharing Plan].
 

	
All the data being shared will be detailed in the data user agreement (DUA).


Statistical Analysis (by Specific Aim)
	
SA 1: We will use results from the REACT-PD study to establish a calibration of tele-visit (TV) assessments to predict in-clinic MDS-UPDRS scores (Aim 1b). Lin's concordance correlation coefficient, <math>r_c</math>, will be used to summarize accuracy of the calibrated TV estimates vs. scores collected from in-person SURE-PD3 visits conducted close in time, accepting TV estimates as sufficiently accurate if <math>r_c > 0.8</math>. If we observe insufficient concordance, we will recalibrate using all available data from both REACT-PD and the current study.
 
SA 2: The study sample will be randomly split 2:1 into calibration and validation subsets. The calibration sample will be used to derive smartphone (SP) measures that best match the TV assessed composite scores of motor function (MDS-UPDRS part 3), non-motor function (MoCA total score), subjective function (including clinical global impression [CGI] scores, patient global impression scores, modified Schwab and England ADL scores, and MDS-UPDRS parts 1b and 2 scores), and estimates of MDS-UPDRS part 1-3 total scores (Aim 2a). The accuracy of calibrated SP measures will be tested in the reserved validation sample using Lin's concordance correlation coefficient, <math>r_c</math>. If we observe insufficient concordance, we will recalibrate using all available data from both the calibration and validation samples.
 
TV assessments and calibrated SP measures of disease progression will be compared generally and between specific subsets of participants expected to progress at different rates (Aim 2b). Each measure will be standardized to 30% of the observed mean change over 2 years based on a random-slopes linear mixed model of the full sample such that a one-unit change of all standardized, calibrated measures would reflect an equivalent magnitude of change relative to natural rates of progression. Estimated measure-specific variance components will be used to estimate the standard error for a treatment group comparison from a two-arm trial assuming an assessment schedule appropriate for a given measure, e.g., annual for TV measures and quarterly for SP measures. The ratio of squared standard errors will be used to estimate the relative sample size required using one or another measure for designs with equivalent power. The same approach will be used to identify measures that are sensitive to biological subgroups (e.g., among participants stratified by their rate of MDS-UPDRS progression over the first 2 years of in-clinic follow-up in the parent trials) or treatment-based subgroups (e.g., participants randomized to isradipine or serum urate elevation). TV assessments and SP measures will also be compared with respect to their accuracy in predicting future clinical events and changes in


	
PROs, e.g., dropping below 80% on the modified Schwab and England ADL, experiencing a fall and other PROs as captured by FI application including PD-PROP measures.
 
SA 3: We will derive novel measures that best predict disease progression using passively collected SP data. We will split the sample 2:1 into discovery and validation subsets, like active tasks. A range of SP measures will be derived from passive data. For walking data (Aim 3a) these include but are not limited to time and frequency domain statistics, energy and entropy of frequency spectrum from the tri-axial accelerometer, along with absolute displacement measurements. For displacement information (Aim 3b) data will be summarized into variables such as furthest distance traveled, frequency of trips, average daily distance etc. Resulting summary metric will then be matched with the TV assessed composite scores of motor function (MDS-UPDRS part 3), Schwab and England ADL scores, MDS-UPDRS (parts 1b and 2 scores), and estimates of MDS-UPDRS part 1-3 total scores. The accuracy of the associations will then be tested in the validation data subset using Lin's concordance correlation coefficient, <math>r_c</math>.
 
Passive measures will be assessed for progression using the same methods as described in SA 2b.


Power Calculations
	
SA 1b. With a sample size of ~10 SURE-PD3 participants expected to complete at least one TV close in time to their in-person clinic visit, the study will have 80% power to conclude that the REACT-PD calibrated tele-visit estimates are sufficiently accurate (<math>r_c > 0.8</math> at <math>\alpha = 0.05</math>) if the true concordance is at least 0.89.
 
SA 2a. With a 2:1 split of ~340 AT-HOME PD participants, yielding ~115 participants contributing to validation tests, the study will have 80% power to declare a given SP measure sufficiently accurate (<math>r_c > 0.80</math> at <math>\alpha = 0.05</math>) if the true concordance is at least 0.87.
 
SA 2b. With approximately 80% of participants participating in the SP portion of the study, yielding ~340 participants contributing to the smartphone vs tele-visit comparison, the study would have an 80% probability of selecting the true preferred measure from a pair of TV or SP if the preferred measure had lower standard error by an effect size of at least 0.065.
 
SA 3. With a 2:1 split of ~240 participants, yielding ~80 in the validation sample and at least 25% experiencing at least an 8-point progression in MDS-UPDRS parts 1-3 total score, the study would have 80% power to declare a novel measure derived from passive SP monitoring to have a ROC AUC significantly greater than 0.80 if the true AUC were at least 0.95.

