We will compare TV vs. calibrated SP measures of disease progression generally, as predictors of future clinical events and changes in patient reported outcomes, and between specific subsets of participants expected to progress at different rates (Aim 2b) due to biology or treatment. After calibration, we will estimate the standard error for a treatment-group comparison from a two-arm trial using measure-specific variance components from a bivariate random-slopes linear mixed model for each pair of TV and SP measures and assuming an assessment schedule appropriate for each measure, e.g., annual for TV measures and quarterly for SP measures. Preferred measures would have smaller standard errors, and specifically, the ratio of squared standard errors provides an estimate of the relative sample size required. We will use the same approach to identify measures that are significantly more sensitive to biological

subgroups (e.g., among participants stratified by their rate of MDS-UPDRS progression over the first 2 years of in-clinic follow-up in the parent trials) or treatment-based subgroups (e.g., participants randomized to Isradipine or serum urate elevation). To compare TV assessments and SP measures with respect to their accuracy in predicting future clinical events and changes in patient reported outcomes, we will use the same 2:1 training: validation split and train separate models using TV and SP metrics collected over the first year of follow-up to predict clinical events and changes in PROs over the second year of follow-up. Clinical events will include dropping below 80% on the modified Schwab and England ADL and experiencing a fall. PROs of interest will include summary scores from the PDQ-8, EQ-5D, and PDAQ-15 and measures derived from the PD-PROP. Selection of the best training models will be based on 10-fold cross-validated accuracy for binary outcomes and residual sum of squares for continuous measures. Positive and negative predictive values of TV and SP-derived predictions will be estimated from the validation sample for binary outcomes and compared by logistic regression. For continuous outcomes, RSS estimates will be compared between TV and SP-derived predictions. As an exploratory analysis, additional models that combine TV and SP measures will be constructed and tested for accuracy relative to models derived from TV or SP measures alone.

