### 13.3 Go/No-go Milestones, Challenges and Opportunities

Our systematic approach to building the study's main tele-health assessment platforms and then sequentially recruiting its sub-cohorts suggests realistic prospects of meeting our project timeline and of reaching pivotal Go/No-go milestones set at 75% of recruitment and retention goals to ensure a reasonable likelihood of accomplishing our SAs. However, in the event that a milestone was not achieved then NINDS program staff would determine in discussion with the SC whether the study should be continued and/or adapted.

Just as our infrastructure plans (under SA1) rely on logistical capabilities, our experimental hypotheses (under SAs 2 and 3) depend on scientific assumptions, which if challenged would lead us to consider contingencies accordingly. For example, the ability to compare disability progression measured by tele-health platforms relies on true disease progression during two years of cohort follow up. However, this period coincides with the so-called 'honeymoon' phase of treatment after DT initiation when observable motor progression may be modest due to early, uncomplicated medication titration (40). Anticipating this possible pitfall, we will incorporate an adjustment for levodopa dose equivalents in our motor score-based progression analysis. We will also explore dopa-resistant cognitive outcomes and would proactively consider options to further extend the cohort into subsequent phases of non-motor and dopa-resistant disability accumulation. In addition, we will remain open to new opportunities to leverage the project's resources; for example, adopting potentially more sensitive wearable technologies in this rapidly evolving mobile health field, or assessing events to which the study cohort may be uniquely suited such as the impact of parent trial results, which should be announced during the follow-up period.

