#### 13.4 Sample Size Determination

SA 1b. With a sample size of ~10 SURE-PD3 and ~50 SUPER-PD participants expected to complete at least one TV close in time to their in-person clinic visit, the study will have 80% power to conclude that the REACT-PD calibrated tele-visit estimates are sufficiently accurate ( $r_c > 0.8$  at  $\alpha = 0.05$ ) if the true concordance is at least 0.89.

SA 2a. With a 2:1 split of ~340 AT-HOME PD participants, yielding ~115 participants contributing to validation tests, the study will have 80% power to declare a given SP measure sufficiently accurate ( $r_c > 0.80$  at  $\alpha = 0.05$ ) if the true concordance is at least 0.87.

SA 2b. With approximately 80% of participants participating in the SP portion of the study, yielding ~340 participants contributing to the smartphone vs tele-visit comparison, the study would have an 80% probability of selecting the true preferred measure from a pair of TV or SP if the preferred measure had lower standard error by an effect size of at least 0.065.

SA 3. With a 2:1 split of ~240 participants, yielding ~80 in the validation sample and at least 25% experiencing at least an 8-point progression in MDS-UPDS parts 1-3 total score, the study would have 80% power to

declare a novel measure derived from passive SP monitoring to have a ROC AUC significantly greater than 0.80 if the true AUC were at least 0.95.

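### Aim 2b's relative sample size ignores the direction of mean change and the sampling error of its divisor, and Section 13.2 omits the standardisation step

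*Combined protocol and SAP*

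**What the plan says.** The Synopsis (Statistical Analysis, SA 2) sets out the comparison of tele-visit (TV) and smartphone (SP) measures in three steps.

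- Scaling: "Each measure will be standardized to 30% of the observed mean change over 2 years", estimated from a random-slopes mixed model. The purpose is that one unit on every measure "would reflect an equivalent magnitude of change relative to natural rates of progression".
- Standard error: measure-specific variance components give the standard error of a two-arm comparison under each measure's own schedule, for example "annual for TV measures and quarterly for SP measures".
- Comparison: "The ratio of squared standard errors will be used to estimate the relative sample size required".

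Section 13.2 describes the same comparison using "measure-specific variance components from a bivariate random-slopes linear mixed model". It says that "Preferred measures would have smaller standard errors" and that the ratio of their squares estimates relative sample size. It does not mention scaling to 30% of the mean change.

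Neither text sets a condition on the direction of the mean change or gives an interval for the ratio. Section 13.3 warns that "observable motor progression may be modest due to early, uncomplicated medication titration" and adds a levodopa-equivalent adjustment for motor-score analyses. Section 13 leaves further detail to a separate SAP, which is not among the documents reviewed.

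**The concern.** The scaling is meant to put every measure on a common footing of natural progression. As written it has two gaps.

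1. **Direction.** The divisor is squared, so its sign is lost. The measures also run in different directions: per Section 6.1, higher is better on MoCA and Schwab and England, while higher is worse on the global impression scales. Treated participants are rated in the usual ON state, and cognitive app tasks recur over nine sessions. An average improvement on some measure therefore cannot be ruled out in advance.
2. **Divisor error.** The observed mean change is an estimate. When it is small relative to the SD of individual change, its sampling error dominates the ratio. The stated calculation uses variance components only.

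The ratio is how Aim 2b identifies a preferred measure on efficiency. The same approach is carried to biological and treatment subgroups, where samples are smaller, and to the passive measures of Aim 3 (about 240 participants).

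**Working it through.** **The plan's own figure.** Section 13.4 has "yielding ~340 participants contributing to the smartphone vs tele-visit comparison" and an 80% probability of selecting the better measure at an effect size of 0.065. The plan gives no formula. A selection calculation with no significance test reproduces it: z(0.80) × √(2/n) = 0.8416 × √(2/340) = 0.0645. At 0.065 the probability is 0.802. That formula has no term for error in a mean-change divisor.

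**The stated rule.** Let V be the squared standard error of the treatment comparison on the raw scale and D the observed mean 2-year change. The standardised squared standard error is V/(0.3D)². The relative sample size of SP against TV is

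(V_SP / D_SP²) / (V_TV / D_TV²),

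and the 0.3 cancels.

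**Direction.** Replacing D by −D leaves the ratio unchanged. As an arithmetic illustration only, take equal variances, one measure improving by 0.5 SD and one worsening by 0.3 SD. The ratio is (1/0.5²)/(1/0.3²) = 0.09/0.25 = 0.36, in favour of the improving measure.

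**Divisor error.** Inputs:

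- n = 340 × (1 − 0.15) = 289. The 340 is from Section 13.4. The 15% is the tele-visit dropout in Section 5.1.
- Mean/SD of 2-year change from 0.2 to 1.0: assumed, since the documents give no value.
- Correlation between the two measures' changes of 0.3 or 0.6: assumed.
- Two measures of truly equal efficiency, so the true ratio is 1.

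The two observed mean changes were drawn as bivariate normal with standard error SD/√289. Variances were held at their true values, so the spread below comes from the divisor alone.

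| Mean/SD | 95% range, corr. 0.3 | 95% range, corr. 0.6 | Spurious twofold difference or more, corr. 0.3 (0.6) |
|---|---|---|---|
| 1.0 | 0.76–1.32 | 0.81–1.23 | about 0% (0%) |
| 0.5 | 0.57–1.75 | 0.66–1.53 | 1.7% (0.2%) |
| 0.3 | 0.38–2.7 | 0.48–2.1 | 15% (6%) |
| 0.2 | 0.20–5.1 | 0.29–3.5 | 34% (22%) |

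Hand check at mean/SD 0.5 and correlation 0.3: SE of the log ratio ≈ 2 × √(2 × 0.7/289)/0.5 = 0.278, and exp(±1.96 × 0.278) gives 0.58–1.73, close to the simulated range.

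With all 340 participants and correlation 0.3 the ranges narrow a little, to 0.60–1.67 at 0.5 and 0.41–2.43 at 0.3.

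**Would a significance gate help?** Suppose a measure entered only if the confidence interval for its mean change excluded zero (n = 289, correlation 0.3). At 0.3 SD, 99.8% of pairs pass and the range is essentially unchanged. At 0.2 SD, 86% pass and the range is still 0.30–3.3. At 0.1 SD, the pairs that pass have mean change inflated about 1.6-fold.

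**The case against.** Several points on the other side have force.

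- **The divisor is only in the Synopsis.** Section 13.2 omits it, and without it neither gap arises in this form. This stands, and it is why the two texts must be reconciled. Dropping the step is not a clean escape: a raw standard-error comparison can favour a measure that varies little because it hardly changes.
- **Calibration.** SP measures are trained to match TV scores and checked in a validation sample, and Section 13.2 assesses calibration longitudinally as well as cross-sectionally. A calibrated SP measure that improves while its TV counterpart worsens is therefore a hypothetical that no passage predicts. It remains possible, because matching scores does not guarantee matching change.
- **Small change is not established.** Section 1.1 expects most participants to be approaching 6–7 years from onset, past the treatment honeymoon, while Section 13.3 warns of modest motor change. The documents are mixed. The levodopa-equivalent adjustment helps, but it covers motor scores only and does not carry the divisor's uncertainty.
- **The simulation is a simplification.** It uses a completer mean. The plan's mixed model uses all available data and up to nine SP sessions, so its estimates may be more precise.
- **The ratio is not the only criterion.** Aim 2b also compares the platforms on predicting clinical events and patient-reported outcomes.

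A reader might infer that the ranking will be wrong several-fold, or that an improving measure will be chosen. The documents do not support that. The first needs mean/SD of roughly 0.2 or less, which they do not give. The second needs an average improvement, which they do not forecast.

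**Conclusion.** The point holds in conditional form. Two parts need no assumed data: the Synopsis and Section 13.2 differ on whether the standardisation is applied, and the Synopsis rule is blind to direction. That the divisor is treated as known is read from the stated calculation and from the absence of any interval; the separate SAP could add one. How much this matters depends on the mean/SD of 2-year change. Near 1.0 the divisor adds modest error. At 0.5 two equal measures can look up to about 1.75-fold apart, and at 0.3 or below a spurious twofold difference becomes common enough to mislead. These sizes rest on 289 participants, correlations of 0.3 and 0.6, and a simple mean-change model. The point should be settled before analysis, because it changes what Aim 2b can conclude about a preferred measure.

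**What to change.** 1. State the same standardisation in the Synopsis and Section 13.2, and carry it into the SAP.
2. Orient every measure so that positive change means worsening. If a measure's model-estimated mean 2-year change is not in that direction, report it as showing no measurable progression and give no ratio.
3. Report every relative sample size with a confidence interval from a participant-level bootstrap. Each replicate should repeat the mixed model, the mean-change estimate and the standardisation.
4. Do not name a preferred measure from the point ratio alone.

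Do not add an entry rule requiring the confidence interval for mean change to exclude zero. It leaves the spread almost untouched at 0.3 SD and selects inflated changes when the true change is very small.

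The cost is SAP wording and a bootstrap run. Data collection does not change. Intervals will be wider, and some measures may drop out of the ranking.
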